1. BACKGROUND

Promoting reductions in problem behaviors is common in medical practice wherein at-risk individuals are counseled to make moderate, sustainable changes in lifestyle (e.g., reduced high fat food intake in individuals at risk for myocardial infarction). Reducing the percentage of heavy drinking days in individuals with alcohol use disorder is an accepted intervention target in alcohol addiction treatment, yet for other drug use disorders, *complete abstinence* remains the standard for demonstrating treatment efficacy. Interventions that promote *reductions* in drug use should improve health, biochemical and psychosocial outcomes. Little prospective research has been conducted to demonstrate the benefits of reduced drug use, however. Demonstrating the benefits of reduced cocaine (COC) use would represent a significant advance in treatment development by changing expectations for outcomes from possible interventions. Adopting this outcome would accelerate identification of promising treatments and advance research and practice in the field.

COC use produces a number of health detriments that could be ameliorated by COC use reduction. For example, COC increases heart rate, blood pressure and vasoconstriction, with chronic use producing changes in vasculature that increase the likelihood of myocardial infarction, atherosclerosis and stroke. These changes are likely mediated through dysregulated endothelial and platelet activity produced by COC, which results in physiological sequelae including increased vasospasm and hypertension. COC use also disrupts immune function, resulting in a pro-inflammatory state and abnormal cell-mediated immunity. This cascade can increase vulnerability to contracting infections or exacerbate existing infections. Individuals with COC use disorder (CUD) also experience a range of psychosocial problems including increased likelihood of co-morbid mental health diagnoses, inhibitory control deficits, risky sexual and drug use behavior and unemployment. Complete COC abstinence improves these potentially devastating consequences of COC use. Some research indicates that reduced COC use also benefits these domains, but this effect has not been *prospectively or comprehensively* demonstrated, preventing adoption of reduced use as an efficacy indicator in clinical trials.

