To fill this critical knowledge gap, we propose a randomized, controlled 12-week trial using incentives to reduce COC use, with an additional 24 weeks of follow up. Over 5 years, subjects will be randomly assigned to one of three groups (n=66 completers/group): 1) high value incentives for COC abstinence in which frequency of COC use is expected to be substantially reduced or eliminated, 2) low value incentives for COC abstinence in which frequency of COC use is expected to be reduced or 3) a non-contingent control group, in which frequency of COC use is expected to remain stable. Three specific aims are proposed:

First, this study seeks to demonstrate that reduced COC use improves physiological and biochemical indicators (i.e., biomarkers) of cardiovascular function. Improvements in cardiovascular function will be assessed with physiological measures of cardiovascular fitness (e.g., peripheral arterial tonomotry) and biomarkers of endothelial (e.g., endothelin-1) and platelet (e.g., soluble CD40L) function.

Second, this study seeks to demonstrate that reduced COC use improves physiological indicators and biomarkers of immune function. Improvements will be assessed with a physiological measure (i.e., delayed-type hypersensitivity) and biomarkers of immune function (e.g., tumor necrosis factor- α , microbiome indicators).

Third, this study seeks to demonstrate that reduced COC use improves psychosocial function. Psychosocial improvements will be assessed with standardized observer and self-reported measures of mental health, drug use and risky behavior, as well as validated and sensitive cognitive behavioral tasks.

Our overarching hypothesis is that individuals assigned to the active treatment conditions (i.e., those who reduce their COC use) will display health improvements compared to individuals assigned to the noncontingent control group both during and after treatment. A "dose-response" is expected whereby individuals assigned to the high value condition will display greater reductions in COC use, and consequently greater improvements, relative to the low value group. We further hypothesize that 1) individuals assigned to active treatment conditions will display improvements from baseline through treatment completion and into follow up and 2) biomarker improvements will predict physiological outcomes.

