2. OBJECTIVES

The primary objective of this study is to demonstrate that reduced cocaine use results in improved cardiovascular, immune and psychosocial outcomes.

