urine sample outcome. Subjects will earn \$60 for each Post Intervention visit. Subjects will also earn \$15 for completing a follow up visit to have their DTH response measured 48 hours after their 4, 12 and 24 Week Post visit. To increase completion rates, subjects will receive half of the visit payment (e.g., \$30 for the 6 Week visit) at the end of each study visit. The remaining half will be paid upon study completion. If a subject completes all study visits, he or she can earn approximately \$1,230 in study payments.

Data Analysis

The statistical significance criterion is $p \le 0.05$.

Aim 1: To demonstrate that reduced COC use improves physiological and biochemical indicators (i.e., biomarkers) of cardiovascular function. Time-and group-varying weekly number of BE-negative urine samples will be analyzed as the primary predictor of cardiovascular outcomes (e.g., endothelin-1 levels) using generalized linear mixed models (GLMM; Stata 14, College Station, TX). All models will be constructed using intent-to-treat analyses including non-completing subjects, whereby the group to which the participant is randomized will be utilized. GLMM are particularly well suited for analyses of longitudinal data, as they allow for multiple observations over time, correlations among observations within an individual subject, for subjects measured at different time points and for baseline covariates (e.g., sex; age; race) and covariates that change over time (e.g., alcohol use). Although GLMM allow for missing data, any missing data will first be tested to determine whether they are missing at random or missing not at random (MNAR). Any data MNAR will be subject to multiple imputation.

Aim 2: To demonstrate that reduced COC use improves physiological indicators and biomarkers of immune function. Time- and group-varying weekly number of BE-negative urine samples will be analyzed as the primary predictor of immune outcomes (e.g., IL-10 levels) using GLMM. Other details are the same as for cardiovascular outcomes.

Aim 3: To demonstrate that reduced COC use improves psychosocial function. Time-and groupvarying weekly number of BE-negative urine samples will be analyzed as the primary predictor of psychosocial outcomes (e.g., other drug use) using GLMM. Other details are the same as for cardiovascular outcomes.

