Other Analyses: This study will gather a rich data set of drug use indicators in addition to our primary indicator of weekly number of BE-negative urine samples. As such, analyses with other COC use indicators such as self-report from the TLFB and ASI, along with overall percentage of BE-negative urines and absolute number of BE-negative urines, will also be conducted to evaluate how COC use reductions indicated on those measures produce beneficial health outcomes. Inter-relationships between biomarker and physiological outcomes will be assessed using correlational analyses to determine how biomarker improvements predict physiological improvements from data collected at the same time point (e.g., cardiovascular biomarkers and ECG outcomes from Week 12), as well as from biomarker outcomes that precede physiological assessments (e.g., cardiovascular biomarkers from Week 6 and ECG outcomes from Week 12). Other planned exploratory analyses include comparison of our findings to any available normative data (e.g., lab normal ranges for ranges for CRP) to better demonstrate clinically meaningful improvements produced by COC use, as well as evaluation of reduction thresholds whereby subjects will be grouped based on percentage of BE-negative samples across the trial (i.e., 0-25%, 26-50%, 51-75% and 76-100% negative across the trial).

Sample Size Justification

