The physiological and biological cardiovascular function tests will be the primary outcome measures from the intervention and follow up period because cardiovascular insult is one of the most troubling health problems associated with COC use. As such, previously published data regarding the effects of COC use reduction on endothelin-1 levels were used to estimate the necessary sample size for this trial. In that study, reduced COC use significantly reduced endothelin-1 levels (estimated effect size [r]=0.28), approximately half of that observed after COC abstinence. Although cardiovascular measures will be our primary outcome, it is important to note that comparable effect sizes have been observed for indicators of psychosocial outcomes as a function of reduced COC use. Effect sizes observed following COC use reduction in those studies ranged from approximately 0.15 to 0.45 for statistically significant outcomes (e.g., improved ratings of "Good Functioning" after treatment, reduced alcohol use at the end of treatment). Enrolling 66 completing subjects in each group will give us 80% power (alpha=0.05) to detect effect sizes (r) as small as 0.14 when comparing

data across the three groups. This sample size will also allow us to conduct exploratory analyses and control for any relevant biological variables that might influence outcome. Dependent variables are continuous, increasing our power relative to using dichotomous variables.

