15. PAYMENT

In total, subjects can earn \$1980 in the high value group and \$468 in the low value group if they are completely abstinent throughout the trial, although this is unlikely given previous findings. Subjects assigned to the control condition will receive \$13 per urine sample they provide independent of test results. Subjects will earn \$15 for 3 Days/Week visits, \$30 for Weekly visits, \$45 for 4 Week visits and \$60 for the 6 Week visits, in addition to any payment they receive for their urine sample outcome. Subjects will earn \$60 for each full Post Intervention visit and \$15 for visits in which their DTH response is evaluated (i.e., follow up visits 48 hours after the 4, 12 and 24 Weeks Post Intervention visit; these visits are expected to last 30-60 minutes). To increase completion rates, subjects will receive half of the visit payment (e.g., \$30 for the 6 Week visit) at the end of each study visit. The remaining half will be paid upon study completion. If a subject completes all study visits, he or she can earn approximately \$1,230 in study payments.

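### The primary model has no term separating abstinence from partial reduction, so a benefit confined to abstinent subjects could be reported as a benefit of reduced use

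*Combined protocol and SAP*

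**What the plan says.** Section 1 (Background) treats one fact as settled: "Complete COC abstinence improves these potentially devastating consequences of COC use". It presents the benefit of reduced use as not yet shown prospectively. Section 2 (Objectives) builds the trial on that gap: "The primary objective of this study is to demonstrate that reduced cocaine use results in improved cardiovascular, immune and psychosocial outcomes".

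Section 7, Data Analysis, names a single primary predictor, the weekly number of BE-negative samples out of three, in a generalized linear mixed model: "Time-and group-varying weekly number of BE-negative urine samples will be analyzed as the primary predictor of cardiovascular outcomes". Aims 2 and 3 repeat this for immune and psychosocial outcomes. The text does not say whether the count enters as linear or categorical. It includes no abstinence indicator, no analysis of continuing users and no test of shape.

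Two places bear on how many abstinent subjects to expect. Section 1 says that in the high value arm "frequency of COC use is expected to be substantially reduced or eliminated". Section 15 (Payment) gives the maximum earnings for subjects "if they are completely abstinent throughout the trial, although this is unlikely given previous findings". Neither gives a share.

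The nearest thing to a separation is exploratory. Section 7, Other Analyses, groups subjects as "0-25%, 26-50%, 51-75% and 76-100% negative across the trial". The Sample Size Justification cites an endothelin-1 effect of r=0.28 for reduced use, described as "approximately half of that observed after COC abstinence".

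**The concern.** The count runs from no negative samples in a week to all three. Subjects who have stopped sit at 3 throughout; those who have cut down are spread over the range. If only the first group improves, its members still pull the fitted association in the favourable direction, because they occupy the top of the scale. This would be so even if the urine count tracked use perfectly. It comes from the model, not from assay sensitivity.

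What is at stake is the inference. The trial is meant to support reduced use as an endpoint in its own right. If its primary test can be passed through an effect that the Background already grants to abstinence, a positive result does not by itself establish the Section 2 objective.

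**Working it through.** **Figures taken from the plan.** Three samples a week for 12 weeks is 3 × 12 = 36, which agrees with the Payment section (36 × $55 = $1,980; 36 × $13 = $468). For the bands, 27/36 = 75.0% and 28/36 = 77.8%, so the top band holds subjects with 28 to 36 negatives. A subject with eight positive samples shares it with a fully abstinent one.

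The plan's detectable effect of r=0.14 is not reproduced by a simple two-sided correlation with 198 completers: tanh[(1.960+0.842)/√195] = 0.198. A repeated-measures calculation with unstated inputs can reach about 0.14, so the figure is not shown to be wrong. Nothing below depends on it.

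**Effect sizes.** Using d = 2r/√(1−r²), which assumes two equal groups:
- r=0.28: d = 0.56/√0.9216 = 0.58.
- If the plan's *half* refers to r, abstinence has r=0.56: d = 1.12/√0.6864 = 1.35.

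**Simulation inputs.** From the plan: 66 completers per arm, endothelin-1 at Weeks 6 and 12, alpha 0.05 (taken as two-sided). Assumed: within-subject correlation 0.5, the abstinent shares, the distribution of negative samples among non-abstinent subjects, a linear count, and no benefit at all below abstinence.

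**Model 1.** Random intercept with a visit effect; negative-sample probability in non-abstinent subjects drawn from Beta(0.8, 1.6); 1,000 trials per scenario. Percentage of trials with a significant favourable slope:

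| Overall abstinent share | d=0.58 | d=1.35 |
|---|---|---|
| 2% | 6% | 12% |
| 3.3% | 8% | 21% |
| 5% | 10% | 36% |
| 10% (control/low/high 5/10/15%) | 25% | 80% |
| 23% (5/20/45%) | 69% | 100% |

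**Model 2.** Regression on subject means as a stand-in for the mixed model; mean negative rates of 20/35/45% (control/low/high) among non-abstinent subjects; 2,000 trials per scenario:

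| Control/low/high share (mean) | d=0.58 | d=1.35 |
|---|---|---|
| 0/5/10% (5%) | 13% | 43% |
| 2/10/20% (10.7%) | 30% | 89% |
| 5/15/30% (16.7%) | 55% | 99% |
| 5/20/40% (21.7%) | 68% | 100% |

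A third simulation, at overall shares of about 2%, 5%, 10% and 23%, gave 5%, 14%, 33% and 80% at d=0.58, and 17%, 53%, 90% and 100% at d=1.35.

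**With abstinence separated.** In Models 1 and 2, adding an abstinence term or leaving abstinent subjects out gives rejection in 4-6% of trials counting both directions (nominal 5%). In the third simulation the term gives 2-3% in the favourable direction (nominal 2.5%).

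**Price of separating.** Under the Model 2 shares, about 155 to 188 of 198 completers are non-abstinent. Counting lost subjects only, the detectable r rises from 0.198 to between tanh(2.802/√185) = 0.20 and tanh(2.802/√152) = 0.22. That understates the cost, because the top of the exposure range is lost too. With a truly graded benefit of d=0.58 over the full range, power fell from 84-94% to 67-81% in one simulation and from 55-76% to 27-29% in another. The loss depends strongly on how the graded benefit is modelled.

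**The case against.** The best defence has four parts.

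**Few abstinent subjects.** The Payment section calls complete abstinence throughout the trial unlikely. This limits the size: at a 2% share the problem is small. But that remark concerns all 36 samples and carries no figure. Abstinence over the weeks before a blood draw is a weaker condition and may be commoner, and Section 1 plans for some use to be eliminated.

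**Evidence of a graded effect.** The study cited for sample size reported a significant benefit of reduction, and Section 1 hypothesises a dose-response, which a count predictor suits. So the simulated case, with nothing gained below abstinence, runs against the only evidence the plan cites. That is fair. It makes the case a test of what the model can distinguish, not a prediction.

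**The randomized arms.** Low value against control is the design's nearest contrast for partial reduction. It helps only in part. Both active arms pay for negative samples, so either can contain abstinent subjects, and no pairwise test is specified.

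**The exploratory bands.** A benefit seen only in the top band would be a warning. But the bands are exploratory and the top one mixes abstinent with near-abstinent subjects. Entering the weekly count as categories would isolate weeks with three negatives, not sustained abstinence, and the plan does not say it will be done.

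A reader might infer that the primary slope will be significant whenever abstinent subjects do better. The figures do not support that: at d=0.58 most simulated trials with a share of 10% or less show no significant slope. A reader might also infer that every reduced-use claim must rest on the slope among non-abstinent observations. The power loss argues against that, since a real graded benefit could then be missed.

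**Conclusion.** The point holds as a limit on what the primary analysis can show. A significant slope on the weekly count is compatible with a graded benefit of reduction and with a benefit confined to abstinence, and nothing pre-specified as primary tells them apart.

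The chance of a favourable result from abstinence alone runs from about 5% to 80% at d=0.58 and from roughly 12% to 100% at d=1.35. These ranges rest on assumed overall abstinent shares of about 2% to 23%, assumed use patterns in the remaining subjects, and no benefit below abstinence. The larger effect also assumes that the plan's *half* refers to r rather than to the change in endothelin-1. The documents fix none of these, so the upper figures should not be quoted alone.

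This should be fixed, but it does not invalidate the primary model. The documents do not support saying that a positive result would necessarily be an abstinence effect.

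**What to change.** Keep the planned primary model and add the following to Data Analysis:

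- For each of the three aims, pre-specify a key supporting analysis that adds an abstinence term (for example, every sample since the previous assessment BE-negative) or tests departure from linearity in the count.
- Report the slope among non-abstinent observations beside the abstinence effect, both with intervals.
- State that a significant slope in the primary model does not, alone, show a benefit of reduction short of abstinence.
- Under Other Analyses, split the top band into 76-99% and 100%.

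This is a change of wording and uses data already planned. The cost is in interpretation. The separated slope rests on fewer observations and a narrower range, so a null result there does not rule out a graded benefit. It is also associational, because abstinence arises after randomization; the same is true of the weekly count itself. The plan should say both.

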After screening, consenting subjects deemed eligible will be enrolled in a 12-week intervention, with a 24week post intervention follow up period. Subjects will be urn-randomized to one of three groups: 1) high value incentives, 2) low value incentives or 3) non-contingent control. An urn randomization process will be used to assign subjects to the three conditions. This method is designed to balance groups on important biological variables that may independently influence outcome. Subjects will be randomized based on sex (male/female), age (>35/≤35 years) and COC use (>15/≤15 days used in the past 30). These characteristics will be determined based on responses to the ASI completed during screening. [name] will perform the randomization and notify non-blind study staff of group assignment. Subjects will be assigned 1:1:1 to the high value, low value and non-contingent control groups.

Alternative Reinforcers for Reduced COC Use: Schedules of Reinforcement and Procedures

Subjects will be assigned to one of two schedules of reinforcement (high and low value incentives) for providing BE-negative urine samples or to a non-contingent control group who will receive money for simply providing a urine sample at each visit.

Subjects assigned to the high value condition will receive \$55 for providing a BE-negative urine sample. Subjects assigned to the low value condition will receive \$13 for providing a BE-negative urine sample. Providing a BE-positive urine sample will result in no payment for that sample in either the high or low value group. Subjects assigned to the control condition will receive \$13 per urine sample they provide independent of test results. Subjects will also be paid for attending study visits during the protocol (see below), independent of urine result outcome, to increase attendance and minimize missing data.

The nature of the intervention prevents subjects from being blind to their assigned condition (i.e., subjects need to be told whether they will earn money for BE-negative urine samples or will earn money for simply providing a urine sample), but subjects will be instructed not to discuss the details of their participation with other subjects or study staff. To enhance rigor and reduce bias, study staff who complete post-randomization assessments, as well as the biostatistician, will be blind to the assigned condition for each subject.

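### Baseline cocaine use and the baseline outcome are not named in the models, so starting severity can pass as a benefit of reduced use

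*Combined protocol and SAP*

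**What the plan says.** **Randomisation (Section 7, Random Assignment).** "Subjects will be randomized based on sex (male/female), age (>35/≤35 years) and COC use (>15/≤15 days used in the past 30" days. The reason given is: "This method is designed to balance groups on important biological variables that may independently influence outcome". The values come from the ASI at screening.

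**Analysis (Section 7, Data Analysis, Aim 1).** The time- and group-varying "weekly number of BE-negative urine samples will be analyzed as the primary predictor of cardiovascular outcomes (e.g., endothelin-1 levels"). Generalised linear mixed models are chosen because "they allow for multiple observations over time, correlations among observations within an individual subject", and because they can take "baseline covariates (e.g., sex; age; race") as well as time-varying ones, with alcohol use as the example. The analysis is called intent-to-treat, "whereby the group to which the participant is randomized will be utilized". Aims 2 and 3 refer back to Aim 1 for all other details.

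**Sample Size Justification.** The sample size is said to allow the team to "control for any relevant biological variables that might influence outcome". No variable is named there.

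**Baseline data.** Table 1 schedules biomarkers, DTH, PAT and ECG at baseline, and Section 1 hypothesises improvement from baseline. The analysis text does not say whether the baseline value enters the model as a covariate, as a response, or not at all.

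**The concern.** The plan treats past-30-day cocaine use as prognostic: that is why it is in the urn. Balancing the arms on it protects comparisons between arms. It does not protect a regression of outcome on the number of negative urines achieved, because subjects within each arm sort themselves on that count.

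Take two subjects in the same arm, one using 5 days a month at entry and one using 25. The first can give more negative samples with little change in behaviour and may have entered with better endothelial markers. If starting use is not in the model, that difference is credited to reduction during the trial. A random intercept does not cure this, since the fitted coefficient still draws on differences between subjects.

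What is at stake is the main claim in Section 2, that reduced use itself improves health. The same gap runs through all three aims.

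**Working it through.** **1. Named covariates against what is available at entry.**

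| Variable | Urn factor | Named as an example covariate |
|---|---|---|
| Sex | yes | yes |
| Age | yes | yes |
| Cocaine-use days, past 30 | yes | no |
| Race | no | yes |
| Baseline value of the outcome | no | no |

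**2. The plan's own figure.** The plan gives no figure for covariate adjustment. The nearest yardstick is r = 0.14, which the Sample Size Justification says 66 completers per group can detect with 80% power. As a two-sided correlation test on 3 × 66 = 198 subjects, power is Φ(atanh(0.14) × √195 − 1.96) = Φ(1.968 − 1.960) ≈ 0.50. So 80% is not reproduced by this test; it may rest on an unstated repeated-measures calculation. That is a separate matter, and 0.14 serves here only as a scale.

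**3. Rough size of a spurious association.** With no true effect, and starting use the only link between count and outcome, the induced correlation is the product of the two links. Neither link is in the documents. Assume −0.3 to −0.6 between baseline use and negative urines, and 0.2 to 0.4 between baseline use and endothelin-1:

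- weakest: −0.3 × 0.2 = −0.06
- strongest: −0.6 × 0.4 = −0.24

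The range includes the plan's 0.14 in absolute size. This is a cross-sectional sketch, so a longitudinal check follows.

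**4. Simulation with no true effect.** 198 subjects, outcome at Weeks 6 and 12, exchangeable within-subject correlation, effect of the urine count set to zero, 1,000 runs per scenario, test at 5%. Baseline use was dichotomised, as in the urn. The severity strengths are assumptions.

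| Confounding | No adjustment | Baseline use only | Baseline outcome only (covariate) | Both |
|---|---|---|---|---|
| None | 4.8% | 4.9% | 4.8% | 5.1% |
| Weak | 7.4% | 6.7% | 5.9% | 5.8% |
| Moderate | 14.1% | 6.8% | 10.1% | 7.4% |
| Strong | 37.3% | 10.0% | 16.4% | 6.7% |

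Simulation error is √(0.074 × 0.926 / 1000) ≈ 0.8 percentage points at 7.4% and √(0.373 × 0.627 / 1000) ≈ 1.5 points at 37.3%. The weak-case gap is therefore small against the noise; the moderate and strong gaps are not. In the strong case, adjusting for one variable alone leaves a clear excess.

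**5. Bias.** The mean coefficient, which should be zero, moved from −0.016, −0.040 and −0.075 (weak, moderate, strong; no adjustment) to −0.005, −0.009 and −0.015 with both. The share removed is 1 − 0.005/0.016 ≈ 69%, 1 − 0.009/0.040 ≈ 78% and 1 − 0.015/0.075 = 80%.

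**6. Form of the baseline outcome.** Without confounding, the standard error of the predictor was 0.046 with no adjustment, 0.046 with baseline use, 0.038 with baseline outcome as a covariate and 0.038 with baseline as a repeated response row. In the strong case the response row on its own gave 16.9% false positives, close to the 16.4% for the covariate. The response row together with baseline use was not simulated.

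**The case against.** The strongest reply is that the covariate text is an open list. It says what mixed models can accommodate and gives examples, so it cannot be said to leave a variable out of a fixed set. That stands. The Sample Size Justification also speaks of controlling for relevant biological variables, in wording close to the reason given for the urn factors, so the authors may well intend to adjust for baseline use. But that sentence says what the sample size permits, not what will be fitted.

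A second reply is that baseline may already be in the model as one of the repeated measurements. The text allows this, and the precision of the predictor would then match covariate adjustment. This also stands. It does not answer the confounding point: in the strong scenario the response row alone left 16.9% false positives. It also needs a stated rule for the predictor at baseline, because the weekly count exists only during the intervention.

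A third is that the entry criteria (a cocaine-positive urine and moderate to severe disorder) narrow the range of severity. They may, but an urn cut at 15 days implies that subjects are expected on both sides.

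Three stronger readings are tempting and not supported:

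- A reader might infer that the model ignores its randomisation scheme. It does not: sex, age and randomised group are all mentioned, although the role of group is not spelled out.
- A reader might infer that race was put in place of cocaine use. Nothing in the documents shows a substitution.
- A reader might infer a definite loss of precision. That would follow only if baseline were left out of the model altogether, which the plan does not say. The urn factor gave no visible precision gain in the simulation.

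**Conclusion.** The concern holds as a gap in a model whose predictor is not randomised. Under the assumed severity effects, the false-positive rate for the primary predictor runs from about 7% to 37% without adjustment, and about 6% to 7% with baseline use and baseline outcome both in the model.

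These figures show direction and range only. The true strength of the severity effects cannot be read from the documents. The unadjusted model stands in for one with only the named covariates, which assumes that those covariates carry little information about starting severity. If baseline severity is only weakly related to the urine count or to the outcome, the harm is slight.

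Adjustment does not remove the problem. Baseline use is self-reported, and other differences between subjects who do and do not achieve negative urines remain. The coefficient would still be an association, not a randomised effect.

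**What to change.** In Section 7, Data Analysis, replace the examples with a stated set for all three aims:

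- sex, age in years and cocaine-use days in the past 30 at screening, with age and days entered as continuous values and not only as the urn categories;
- the baseline value of the outcome, entered once: either as a covariate in a model for post-baseline outcomes, or as a repeated response row, but not both. If it is a response row, state what value the urine-count predictor takes at baseline;
- race may stay as an additional covariate.

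The cost is a few sentences of analysis text, settled before the data are analysed. Cocaine-use days and age are already obtained for the urn, and baseline outcomes are already scheduled in Table 1. No new visit, assay or subject is needed.
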